## Background

Tramadol is a commonly used opioid analgesic for the treatment of moderate to severe acute and chronic pain. It is metabolized in the liver by O- and N-demethylation (phase I) and conjugation (phase II). O-demethylation of tramadol to the active metabolite O-demethyltramadol (ODT) is catalyzed by cytochrome CYP2D6, and N-demethylation to N-demethyltramadol (NDT) occurs via CYP2B6 and CYP3A4. The ODT metabolite of tramadol is an active metabolite that has 200-fold higher affinity for opioid receptors than tramadol itself and is thought to be responsible for the bulk of the analgesic effect of tramadol. CYP2D6 is a non-inducible enzyme, and its gene shows marked polymorphism due to which there are large individual and population differences in metabolism, analgesic action, and side effects of tramadol. Individuals carrying two inactive copies of CYP2D6 are poor metabolizers (PM) of tramadol compared to those carrying two copies of the extensive wild allele (EM). Individuals carrying one or more copies of inactive alleles or alleles of reduced CYP2D6 activity are intermediate metabolizers (IM), and those carrying more than two copies of wild alleles for CYP2D6 are ultrarapid metabolizers (UM). In addition to pharmacogenetics, the functional status of the liver and kidneys plays an important role in the pharmacokinetics of tramadol. Tramadol and the ODT metabolite are excreted by the kidneys, therefore renal failure, which is common in intensive care units (ICU), leads to the accumulation of tramadol and the ODT metabolite in the blood. More than 80% of tramadol is metabolized in the liver. There are known to be significant differences in the pharmacokinetics of tramadol between healthy subjects and patients with hepatic failure. In patients with hepatic failure, tramadol plasma concentrations are higher and the elimination half-life is longer. These changes are primarily due to decreased hepatic elimination. Patients in ICU often have mildly reduced liver function as part of multiorgan failure due to sepsis or Systemic Inflammatory Response Syndrome (SIRS), while major abdominal surgery and anaesthesia reduce liver perfusion and contribute to hypoxic liver damage. Drug distribution changes as a result of decreased protein production and changes in extracellular volume, and the activity and metabolic capacity of liver enzymes decreases resulting in increased concentration and decreased plasma elimination of drugs, which is often very difficult to predict. The CYP2D6 genotype-phenotype has been shown to be relatively effective in clinical practice, but it should be noted that a number of genotype-phenotype discrepancies have been documented, therefore the absorption, distribution, metabolism and excretion of tramadol cannot be determined by a single protein genotype. The expression and activity of CYP2D6 is regulated by a number of physiological, pathological and environmental factors. CYP2D6 expression is susceptible to changes in infection states or systemic inflammatory response associated with elevated cytokine values. Expression of CYP2D mRNA and protein is reduced by proinflammatory cytokines in the liver of mice and rats, while administration of anti-inflammatory cytokines such as IL-10 reduces CYP3A activity. This decrease was not observed for CYP2D. At low CYP2D6 activity or when O-demethylation of tramadol is reduced, tramadol is primarily metabolized by N-demethylation. A study in cancer patients known to have a chronic inflammatory condition accompanied by elevated values of proinflammatory mediators showed that elevated IL-6 values correlated with N-demethylation of tramadol and patient tolerance to the analgesic effect of tramadol. Surgical stress, anaesthesia, starvation, postoperative pain, emergency surgery, and surgery for malignant diseases contribute to the development of a systemic inflammatory response. Hypothermia or hyperthermia, leucocytosis or leukopenia, tachycardia and tachypnoea, are clinical components of SIRS which is often difficult to distinguish clinically from acute inflammation, but in both conditions

there is an increase in proinflammatory cytokines, CRP, and PCT. During the first 24 hours, SIRS is common and is not a good predictor of a patient's final outcome, but if the proinflammatory response lasts longer than 24 hours, then it is associated with higher mortality. In addition to elevated values of proinflammatory cytokines, CRP, and PCT, low cholinesterase values in elderly patients are a good indicator of a systemic inflammatory response due to infection, SIRS, and trauma and are an independent risk factor for poor hospital outcome. Decreased serum cholinesterase in the development of SIRS occurs before the rise in CRP, and it is a good marker of early detection of the systemic inflammatory response. Mild or subtle hepatic dysfunction is often seen in patients in intensive care units due to hepatocellular damage caused by hypoxemia due to decreased hepatic flow and degranulation of neutrophils into hepatic sinusoids in sepsis or SIRS. Therefore, the metabolism and analgesic effect of tramadol in ICU patients after major surgeries will depend on a number of factors. On the one hand of the polymorphism of the CYP2D6 gene, and on the other of the state of important organ systems involved in the metabolism and elimination of tramadol, as well as the development of a systemic inflammatory response that alters cytochrome activity.

### **Design of a research**

The research will be designed as a prospective observational research. The research will include patients hospitalized at the Department anaesthesiology and intensive care unit (ICU) of the Clinical Hospital Osijek, and after the signed informed consent. Informed consent will be signed by the legal guardian if the patient is unable to do so alone for various reasons.

### **Objectives**

1. measure the plasma concentrations of tramadol, O-demethyltramadol and N-demethyltramadol in a patient admitted to the intensive care unit (ICU) after major abdominal surgery;
2. examine differences in tramadol, ODT and NDT concentrations with respect to CYP2D6 gene polymorphism;
3. examine the effect of systemic inflammation on the concentrations of tramadol, ODT and NDT in the early postoperative period;
4. examine the analgesic effect of tramadol with respect to systemic inflammation and organic dysfunction.

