After signed informed consent, all patients included in the study will have a blood sample taken for analysis of the CYP2D6 polymorphism, and ultrafast and slow metabolizers will be excluded from further analysis. A commercial set of "High Pure PCR Template Preparation Kit" according to the manufacturer's instructions (Roche Life Science) will be used to isolate the genomic DNA of the subjects. DNA isolation will be performed from whole blood samples with the anticoagulant EDTA. The protocol consists of lysis of blood cells using lysis buffer, degradation of protein by proteinase K, separation of DNA molecules from the mixture, and purification of DNA using glass mesh columns in a series of washing and centrifugation steps. Measurement of the isolated DNA concentration will be performed using a UV / VIS nanospectrophotometer. DNA samples will be stored at -20 oC until the testing procedure. To determine the allelic variants CYP2D6 \* 3 (rs35742686), CYP2D6 \* 4 (rs3892097) and CYP2D6 \* 5 (whole gene deletion), the commercial set LightMix Kit CYP2D6 \* 3 \* 4 \* 5 / \* 5 will be used according to the manufacturer's instructions (TibMolbiol). The method is real-time PCR (real-time polymerase chain reaction). The test is based on the use of a certain type of fluorescently labeled hybridization assays, the so-called "SimpleProbe" that specifically binds to a sequence that includes a targeted change in DNA. Commercial sets "CYP2D6 TaqMan Copy Number Assay" and "TaqMan Copy Number Reference Assay" according to the manufacturer's instructions (Applied Biosystems) will be used to determine duplication / amplification and the number of copies of the CYP2D6 gene (CYP2D6 \* 1xN). The method is real-time PCR, and the assay is based on the use of fluorescently labeled specific TaqMan probes that bind to the target gene sequence and reference TaqMan probes that bind to a reference sequence that is known to be present in the diploid genome. Relative quantification of the number of copies of the CYP2D6 gene will be possible by analyzing the results using CopyCaller (Applied Biosystems).

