### **Statistical analysis plan:**

Category data will be presented in absolute and relative frequencies. Numerical data will be described by the arithmetic mean and standard deviation in the case of distributions following the normal, and in other cases by the median and limits of the interquartile range. Differences in category variables will be tested by the  $\chi^2$  test and, if necessary, the Fisher exact test. The normality of the distribution of numerical variables will be tested by the Shapiro-Wilk test. Differences of normally distributed numerical variables between two independent groups will be tested by Student's t test, and in case of deviation from normal distribution by Mann-Whitney U test, while in case of 3 or more groups will be tested by analysis of variance (ANOVA, PostHoc Bonferonni, Sheffe), and in case of deviation from the normal distribution by the Kruskal-Wallis test (PostHoc Conover). The correlation of continuous numerical variables will be evaluated by Pearson's correlation coefficient  $r$ , and in the case of ordinal distribution variables by Spearman's correlation coefficient  $\rho$  (rho). Differences in plasma concentrations of tramadol, O-demethyltramadol and N-demethyltramadol according to measurements (6 measurements) will be tested by analysis of variance for repeated measurements (normal distribution) or by Friedman test (Post-hoc Conover) in case of distributions that do not follow normal. The significance level will be set to Alpha = 0.05. MedCalc Statistical Software version 19.0.5 (MedCalc Software bvba, Ostend, Belgium; <https://www.medcalc.org>; 2019) and SPSS (version 16.0, SPSS Inc., Chicago, IL, USA) will be used for statistical analysis.

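### CYP2D6 group (intermediate v extensive) is known for every analysed patient but is left out of the inflammation analyses for Objectives 3 and 4, at some cost in precision

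*Combined protocol and SAP*

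**What the plan says.** The Objectives section uses genotype once, in Objective 2: "examine differences in tramadol, ODT and NDT concentrations with respect to CYP2D6 gene polymorphism". Objective 3 is to "examine the effect of systemic inflammation on the concentrations of tramadol, ODT and NDT in the early postoperative period" and Objective 4 is to "examine the analgesic effect of tramadol with respect to systemic inflammation and organic dysfunction". Neither of these mentions genotype.

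Under Patients and methods, a CYP2D6 sample is taken from every included patient, and "ultrafast and slow metabolizers will be excluded from further analysis". The analysed set is therefore a mix of IM and EM patients whose group is known.

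The Background says of CYP2D6 that "its gene shows marked polymorphism due to which there are large individual and population differences in metabolism, analgesic action, and side effects of tramadol". It closes by saying that metabolism and analgesic effect will depend on several things at once: "On the one hand of the polymorphism of the CYP2D6 gene, and on the other of the state of important organ systems", and then the inflammatory response.

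The Statistical analysis plan offers chi-square or Fisher tests, two-group tests ("Differences of normally distributed numerical variables between two independent groups will be tested by" the t test, otherwise Mann-Whitney), ANOVA or Kruskal-Wallis, Pearson or Spearman correlation, and repeated-measures ANOVA or Friedman over the six samples. It names no covariate, stratum, regression model or interaction, and it does not assign tests to objectives. The only design figure is "The significance level will be set to Alpha = 0.05".

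**The concern.** Inflamed and non-inflamed patients will be compared across a mixture of two genotype groups that the plan itself expects to differ in tramadol metabolism. Leaving out a known baseline predictor of the outcome has one direct consequence: the spread between IM and EM counts as noise. Put another way, if one inflammation group happens to contain more IM patients, the estimate moves for a reason unrelated to inflammation. The study then needs more patients than necessary for the same precision, although the variable that would remove the noise is already in the dataset.

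The argument is strongest for ODT, which CYP2D6 forms. It is weaker for N-demethyltramadol (NDT), which the Background attributes to CYP2B6 and CYP3A4.

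**Working it through.** **No figure to reproduce.** The documents give no sample size, power, SD, IM share or expected effect. Alpha of 0.05 is theirs and is taken as two-sided. Everything else below is an assumption.

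**Assumptions.** IM share of the analysed set p = 0.3 or 0.4; IM level as a fraction of EM k = 0.5 to 0.7; residual log SD s = 0.5 or 0.8; genotype independent of inflammation.

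**Variance inflation from omitting genotype** = 1 + p(1-p)(ln k)² / s².

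| p | k | p(1-p)(ln k)² | s = 0.5 | s = 0.8 |
|---|---|---|---|---|
| 0.3 | 0.7 | 0.21 × 0.127 = 0.027 | +11% | +4% |
| 0.4 | 0.6 | 0.24 × 0.261 = 0.063 | +25% | +10% |
| 0.4 | 0.5 | 0.24 × 0.480 = 0.115 | +46% | +18% |

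**Power** at an assumed 40 per inflammation group and a true inflammation ratio of 0.75 (|ln 0.75| = 0.288), by normal approximation.

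- s = 0.5, adjusted: SE = 0.5 × √(2/40) = 0.112; 0.288/0.112 - 1.96 = 0.61; power 73%.
- s = 0.5, unadjusted, p = 0.4, k = 0.6: SE = 0.112 × √1.25 = 0.125; power 63%.
- s = 0.5, unadjusted, p = 0.3, k = 0.7: SE = 0.112 × √1.107 = 0.118; power 69%.
- s = 0.8, p = 0.4, k = 0.6: SE = 0.179 adjusted and 0.187 unadjusted; power 36% v 34%.

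The gain thus runs from about 10 percentage points to about 2, depending mainly on s.

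**Chance imbalance** (p = 0.4, k = 0.6, 40 per group). The SE of the difference in IM share is √(2 × 0.24/40) = 0.11. Multiplied by |ln 0.6| = 0.511, it gives 0.056 on the log scale, so imbalance alone moves the unadjusted ratio by a factor of about 0.90 to 1.12 (95% range). This is the same loss seen from another side, not an extra one: 0.112² + 0.056² = 0.125² to rounding, the unadjusted SE squared.

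**Does pooling dilute the effect?** Let the inflammation ratio be 0.6 in EM, and let IM have a fraction r of that effect on the log scale. The pooled ratio is exp{[(1-p) + pr] ln 0.6}. For p = 0.3 to 0.4:

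- r = 0 (no effect in IM): 0.70 to 0.74.
- r = 0.5: 0.65 to 0.66.
- r = 1 (equal relative effect): 0.60, no dilution.

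**Does a covariate undo dilution?** No. Take an IM share of 0.35, an EM-IM gap of 0.8 within-genotype SD, an EM effect of 0.6 SD and 50 per group. If the effect is confined to EM, power is 47% unadjusted and 50% with the covariate, because both estimate the same average. The interaction test has about 30% power there, and about 11% if IM keep half the effect.

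**The case against.** Four objections carry weight.

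- **Genotype is already partly controlled.** Excluding poor and ultrarapid metabolizers removes the extremes. The Background's statement about large differences covers the whole polymorphism, so it cannot be used to size the remaining IM-EM gap. This stands, and it is one reason why the gain may be small.
- **The residual spread may be large.** The Background describes renal, hepatic, distributional and inflammatory variation that is hard to predict. At s = 0.8 the power gain almost disappears. This also stands.
- **The omission is by silence.** No test is tied to an objective, and the tests for three or more groups could hold genotype-by-inflammation groups. None are defined, however, and a one-way test on such groups does not by itself give a genotype-adjusted inflammation effect with a confidence interval.
- **Adjustment will be imperfect.** The named assays cover *3, *4, *5 and copy number, while the Background counts reduced-activity alleles as IM. Some IM patients may be labelled EM. This limits the benefit but does not argue against taking it.

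A reader might go further and infer that inflammation acts only in EM patients, so that pooling hides a real effect. The documents do not support this. Under the Background's definition, IM patients can carry one inactive allele or reduced-activity alleles, and nothing says that they have no activity left to lose. The idea that most is lost where there is most to lose describes an absolute fall. A proportional fall gives the same ratio in both groups and no dilution on the log scale.

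**Conclusion.** The point holds as a near-costless gain in precision. As written, the inflammation analyses for Objectives 3 and 4 ignore a baseline factor that is in hand and that the plan itself names as a determinant of the outcome. Under the assumed IM share and IM level, omission inflates the variance by about 11-46% at a residual log SD of 0.5 and 4-18% at 0.8. The true figure is unknown because the documents supply none of the inputs. The calculation concerns log concentrations; nothing was computed for the pain scores in Objective 4.

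It would be wrong to read this as confounding. Genotype is fixed before surgery, and nothing in the documents links it to inflammation. Dilution is conditional: if the relative effect is smaller in IM, the pooled and the covariate-adjusted estimates both understate the EM effect; if it is equal, neither does.

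**What to change.** - **Objective 3:** model log ODT, log NDT and log tramadol (or their ratios) on inflammation with CYP2D6 group (IM v EM) as a prespecified covariate. State how the six samples enter, for example through a mixed model. Report the adjusted inflammation effect with its 95% CI as the main result.
- **Objective 4:** include CYP2D6 group alongside inflammation and organ dysfunction in the analgesia analysis. Low cholinesterase counts towards both of those definitions under Patients and methods, so their separate effects will be harder to tell apart.
- **Secondary and exploratory:** report the inflammation effect within EM and within IM, each with a 95% CI. These are more informative than an interaction p-value and are the only part that addresses a difference between genotypes.
- **Limitation to state:** with the named alleles, some reduced-activity IM patients may be classed as EM, so adjustment is partial.

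The cost is wording in the analysis plan; no new data are needed. The downside is that the within-genotype and interaction estimates will be imprecise and should not be presented as confirmatory.

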### **Patients and methods:**

Patients undergoing major abdominal surgery will be included in the study. A major surgical procedure in the abdomen will be considered all procedures that require a surgical approach by laparotomy, which include resections of parts of the organs of the digestive system. Organic dysfunction will be considered laboratory or clinical signs of decreased renal function measured by diuresis with laboratory increase in serum nitrogen metabolites (increase by  $\geq 30\%$  of normal values), and decrease in liver function measured by increase in liver enzymes (increase by  $\geq 30\%$  of reference values), by a decrease in serum cholinesterase levels ( $\leq 20\%$  of normal), an increase in bilirubin by 30% of normal, or a decrease in synthetic liver function as measured by prolongation of PV to  $\leq 60\%$  of INR. A systemic inflammatory response will involve the perioperative presence of two or more of the following factors: body temperature  $> 38$  oC or  $< 36$  oC, leukocytes  $> 12,000$  or  $< 4,000$  mm^3, pCO2  $< 4.3$  kPa, and pulse  $> 90$  / min. In addition, a perioperative increase in CRP, PCT, and lactate above reference values,

as well as a decrease in serum cholinesterase levels, will be considered a systemic inflammatory response. Patients who have a known allergic reaction to tramadol, and patients who have received tramadol for the past 7 days, patients younger than 18 years, BMI <18 kg / m^2> 40 kg / m^2, and patients who do not sign the informed consent will be excluded from the study. Also excluded from the study will be patients who have had laparoscopic surgery, as well as those on chronic therapy with cimetidine, paroxetine, pimozide, metoclopramide, amiodarone, olanzapine, chlorpromazine, fluphenazine, haloperidol, thioridazine, risoridazine, risoridazine drugs inhibit the activity of CYP2D6 enzyme important in tramadol metabolism.

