After induction under general anaesthesia, in addition to standard laboratory findings, plasma concentrations of albumin, cholinesterase, gamma-glutamyltransferase, bilirubin, C-reactive protein, procalcitonin will be measured, and pH, pO2, pCO2 and lactate values will be determined from an arterial blood sample. During the procedure, patients will be anesthetized by the method of general balanced inhalation anaesthesia with sevoflurane. Postoperatively, vital parameters, such as temperature, pressure, pulse and diuresis, will be continuously monitored in the ICU, and postoperative values of arterial blood gases, lactate and routine laboratory findings - complete blood count - will be determined. In the ICU patients will receive a total of 500 mg of tramadol intravenously divided into 5 doses during the first 24 hours of admission to ICU.

Plasma concentrations of tramadol, O-demethyltramadol and N-demethyltramadol will be measured 1, 2 and 4 hours after the first dose, and immediately before the 2nd, 3rd and 5th doses. In total, therefore, there will be 6 measurements within 24 hours. Determination of the concentration of tramadol and ODT and NDT metabolites from patient

plasma samples will be performed by high performance liquid chromatography (HPLC) on a Shimadzu Nexera XR (Shimadzu Corporation, Kyoto, Japan) on a reverse phase chromatographic system with fluorescence detection (excitation wavelength 200 a emission 301 nm). Separation will be performed on an Agilent Zorbax SB-C8 column, 3.5  $\mu$ m, 4.6x150 mm (Agilent Technologies, Santa Clara, CA, USA) using a mobile phase consisting of methanol and 1.5 mM H3PO4 in a ratio of 19:81), pH 2.5.

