The analgesic effect of tramadol will be measured in patients who are conscious on the NRS scale (0 - no pain, 10 - most severe pain) 30 minutes before and 30 minutes after tramadol administration. An NRS value of 3 or less will be considered adequate analgesia, and in case of inadequate analgesia, an additional analgesic will be used - morphine 2 mg. In patients with impaired consciousness, the analgesic effect of tramadol will be examined by the Behavioral Pain Scale (BPS) (3 - no pain, 12 - most severe pain) and the Critical Care Pain Observation Tool (CPOT). A BPS value of 5 or less will be considered adequate analgesia, as well as CPOT values less than 2. Consumption of additional analgesic will be recorded regularly. Nausea, vomiting, and newly developed respiratory depression will be reported within 24 hours. In all patients, they will record the total time of hospitalization in ZIM, hospitalization and the patient's outcome - death or survival until discharge from the hospital.

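### Objective 4 compares analgesia by inflammation with unadjusted tests only, so differences in the operation and in pre-dose pain can pass for an effect of inflammation

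*Combined protocol and SAP*

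**What the plan says.** The Design section states: "The research will be designed as a prospective observational research". The fourth item under Objectives is to "examine the analgesic effect of tramadol with respect to systemic inflammation and organic dysfunction".

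The Background supplies the link from surgery to inflammation: "Surgical stress, anaesthesia, starvation, postoperative pain, emergency surgery, and surgery for malignant diseases contribute to the development of a systemic inflammatory response".

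Patients and methods defines eligible surgery as "all procedures that require a surgical approach by laparotomy, which include resections of parts of the organs of the digestive system". The only exclusion by type of surgery is of the laparoscopic approach: "Also excluded from the study will be patients who have had laparoscopic surgery". Urgency, malignancy and extent are not restricted, and none of them, nor duration of surgery, is among the data the section says will be recorded.

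There is no group without tramadol: "In the ICU patients will receive a total of 500 mg of tramadol intravenously divided into 5 doses". Pain on the NRS is taken "30 minutes before and 30 minutes after tramadol administration". Adequate analgesia is defined as a level (NRS 3 or less, BPS 5 or less, CPOT below 2), and use of additional analgesic is recorded.

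For group comparisons the Statistical analysis plan gives, for example: "Differences of normally distributed numerical variables between two independent groups will be tested by Student's t test". Its other methods are chi-square or Fisher, Mann-Whitney, ANOVA or Kruskal-Wallis, Pearson or Spearman correlation, and repeated-measures ANOVA or Friedman for the six concentration measurements. It names no regression, ANCOVA, stratification or matching, and no analysis that uses the pre-dose pain score.

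**The concern.** A patient with marked systemic inflammation may have had a longer, more urgent or more extensive operation than a patient without it. A pain level 30 minutes after a dose, a threshold on that level, and rescue use all reflect how much the operation hurts as well as how well the drug works. A crude comparison by inflammation status therefore mixes two things: any difference in response to tramadol, and any difference in the pain that tramadol had to relieve.

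At stake is the interpretation of one of the four stated objectives. A lower rate of adequate analgesia in inflamed patients could be read as inflammation weakening tramadol when it reflects the mix of operations. A larger sample does not help, because the bias stays the same while the standard error shrinks.

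**Working it through.** The documents give no sample size, effect size, SD, case mix or inflammation rate, so there is no planned figure to reproduce. The inputs below are assumptions, chosen to show a range.

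**1. Mixing of two strata.** Assume half the patients have extensive or urgent surgery and half have lesser surgery. Within each stratum inflammation has no effect on analgesia, so the true odds ratio is 1. Then

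P(adequate | inflamed) = Σ P(stratum | inflamed) × P(adequate | stratum),

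and likewise for patients who are not inflamed. With equal strata and 70% v 30% inflamed, P(extensive | inflamed) = 0.35/(0.35 + 0.15) = 0.7 and P(extensive | not inflamed) = 0.15/(0.15 + 0.35) = 0.3.

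| Inflamed (extensive v lesser) | Adequate (extensive v lesser) | Adequate, inflamed | Adequate, not inflamed | Crude OR |
|---|---|---|---|---|
| 60% v 40% | 60% v 70% | 0.6×0.60 + 0.4×0.70 = 0.64 | 0.4×0.60 + 0.6×0.70 = 0.66 | (0.64/0.36)/(0.66/0.34) = 0.92 |
| 70% v 30% | 55% v 75% | 0.7×0.55 + 0.3×0.75 = 0.61 | 0.3×0.55 + 0.7×0.75 = 0.69 | (0.61/0.39)/(0.69/0.31) = 0.70 |
| 80% v 20% | 50% v 80% | 0.8×0.50 + 0.2×0.80 = 0.56 | 0.2×0.50 + 0.8×0.80 = 0.74 | (0.56/0.44)/(0.74/0.26) = 0.45 |

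**2. Pain score.** If tramadol lowers pain by the same number of points in everyone, the spurious difference in post-dose NRS is

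[P(extensive | inflamed) − P(extensive | not inflamed)] × (extra pain after extensive surgery).

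- 60% v 40% inflamed, 1.0 point extra: 0.2 × 1.0 = 0.2 points.
- 70% v 30% inflamed, 1.5 points extra: 0.4 × 1.5 = 0.6 points.
- 70% v 30% inflamed, 2.0 points extra: 0.4 × 2.0 = 0.8 points.

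**3. False-positive rates.** These come from a simulation of 1,500 runs per scenario at alpha 0.05. Pre-dose NRS has mean 5 after lesser surgery, plus the extra above after extensive surgery, with SD 1.5. Tramadol lowers it by 1.75 points (additive) or 35% (proportional), residual SD is 1, and scores are rounded and held within 0 to 10. Inflammation has no effect.

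| Scenario and test | N = 50 | N = 100 | N = 200 |
|---|---|---|---|
| 70% v 30%, +1.5, additive: post-dose NRS, Mann-Whitney | 18% | 33% | 57% |
| Same: adequate analgesia, chi-square | 15% | 25% | 43% |
| 60% v 40%, +1.0, additive: post-dose NRS, Mann-Whitney | 8% | 7% | 12% |

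In the first scenario adequate analgesia appears as about 34% with inflammation and 46% without. Across all confounded scenarios the unadjusted rates for the two level-based outcomes run from 6% to 79%. With extent of surgery in a linear model for post-dose NRS, the rate is about 4% to 7% throughout. That model knew extent exactly; recorded covariates would be proxies and would leave some residual bias.

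**4. Change score.** On the pre-to-post change, the unadjusted false-positive rate stays near 5% if the tramadol effect is additive. If the effect is proportional to pain, at 70% v 30% inflamed patients show a larger fall, by about 0.2 to 0.3 points, with false positives of 8% to 35%. The bias then runs the other way.

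**The case against.** The strongest reply is that the protocol measures NRS before as well as after dosing. A natural reading of analgesic effect is the within-patient change, which makes each patient the reference for how much the operation hurts. With an additive effect that removes the bias. This stands to the extent that bias is not inevitable. It does not rescue the plan: the SAP names no change-score or baseline-adjusted analysis, the adequacy criteria are levels, and with a proportional effect the change score is itself biased.

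Other parts also stand. The documents do not say that larger or more urgent operations hurt more. Eligibility already narrows the range to open digestive resections in patients admitted to ICU, and in the weakest scenario the distortion is trivial (64% v 66%). The objective is worded as an association in a declared observational study, and describing the result that way would meet part of the concern.

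Two stronger readings are tempting and are not supported:

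- A reader might infer that the bias favours the study's own hypothesis. No hypothesis is stated. The Background points both ways: reduced O-demethylation and IL-6-related tolerance suggest less analgesia, while accumulation of tramadol and its active metabolite in renal failure could mean more. The direction also depends on which outcome is analysed.
- A reader might infer that an ineffective drug could be mistaken for one weakened by inflammation. All patients receive tramadol, so its effect is not tested against a control. The relevant null is that inflammation does not alter tramadol analgesia.

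**Conclusion.** The concern holds in a limited form. If the plan is followed as written, the level-based outcomes for Objective 4 are open to confounding by the operation, and nothing in the SAP can separate the two. The surgery-to-inflammation link is the protocol's own; the surgery-to-pain link is a reasonable assumption. The illustrative crude odds ratios of 0.92 to 0.45 show that the distortion may be negligible or substantial. They are not estimates for this study, and the documents do not allow one. Direction is not fixed, because the endpoint is not fixed.

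This is a should-fix: a better analysis is available at small cost, but the objective is one of four, and neither the presence nor the size of the bias is certain.

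**What to change.** In the Statistical analysis plan, give Objective 4 its own prespecified analysis.

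- **Endpoint and model.** Use linear or ordinal regression for the post-dose pain score and logistic regression for adequate analgesia. State which dose or doses are analysed; if several are, allow for repeated measures within patient.
- **Terms of interest.** Include systemic inflammation and organ dysfunction. Low cholinesterase enters both definitions, so the two terms overlap; report each alone as well as together.
- **Adjustment.** Use the pre-dose pain score and a short fixed list known before dosing: elective v emergency, procedure class, duration of surgery, malignancy and age. Fix the list before data are examined, and keep it in proportion to the sample, which the documents do not state.
- **Data.** Add these fields to the recorded data if they are not already captured. Before-and-after timing is stated for the NRS only, so say whether it also applies to BPS and CPOT.
- **Reporting.** Keep the crude comparisons as descriptive. Report the adjusted result as an association: the Background also lists postoperative pain as a contributor to inflammation, and adjusting for the operation cannot remove that reverse path.

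The cost is SAP wording, a few recorded fields and a few degrees of freedom. Treatment does not change.
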